2. BACKGROUND INFORMATION AND SCIENTIFIC RATIONALE

2.1. Background Information

2.1.1. Introduction

Coronavirus disease 2019 (COVID-19) is caused by infection with a novel coronavirus, severe acute respiratory syndrome coronavirus 2 (SARS-CoV-2), which was first detected in Wuhan city, Hubei province, China in 2019. As of June 24, 2022, 539 million cases and 6.3 million deaths attributed to COVID-19 have been reported globally, with 85.5 million cases and 1 million deaths in the US. SARS-CoV-2 is transmitted primarily via respiratory droplets and contact with infectious individuals or fomites¹. COVID-19 commonly manifests with fever, cough, or fatigue, and illness severity ranges from mild (including mild pneumonia) to critical (including acute respiratory distress syndrome [ARDS] and multiorgan dysfunction), with older adults and patients with serious chronic medical conditions at higher risk of adverse outcomes². The mean incubation time from exposure to onset of symptoms is approximately 5 days³. Viral load in posterior oropharyngeal saliva samples is highest in the first week after symptom onset, declining gradually thereafter and remaining detectable for at least 20 days in some patients⁴. It has been observed that the viral load can increase for up to 12 days in naïve patients⁵. SARS-CoV-2 transmission may occur from asymptomatic or pre-symptomatic individuals and is associated with younger age². In addition, high SARS-CoV-2 titers have been detected in oropharyngeal samples early in the disease course⁵,⁶. The current estimated basic reproduction number is 2.2, so SARS-CoV-2 is expected to continue spreading.⁷

¹ WHO, 2020. Modes of transmission of virus causing COVID-19: implications for IPC precaution recommendations. Accessed 2022 June 24. https://www.who.int/news-room/commentaries/detail/modes-of-transmission-of-virus-causing-covid-19-implications-for-ipc-precaution-recommendations.

² CDC, 2020. Interim clinical guidance for management of patients with confirmed coronavirus disease (COVID-19). Accessed 2020 April 3. https://www.cdc.gov/coronavirus/2019-ncov/hcp/clinical-guidance-management-patients.html

³ Zhang et al. Evolving epidemiology and transmission dynamics of coronavirus disease 2019 outside Hubei province, China: a descriptive and modelling study. *Lancet Infect Dis.* 2020 Apr 2. [Epub ahead of print]

2.1.3. ADM03820 Development

ADM03820 drug product is being investigated for the treatment and prevention of COVID-19 in adults. ADM03820 is a 1:1 mixture of two human IgG1 non-competitive binding anti-SARS-CoV-2 antibodies, mAb2130 (YTE+LALA) and mAb2381 (YTE+LALA), individually expressed in a Chinese hamster ovary (CHO) cell line. Several amino acid changes in the Fc region have been incorporated into mAb2130 (YTE+LALA) and mAb2381 (YTE+LALA) to silence or reduce the effector function of antibodies. The LALA variant eliminates complement binding and fixation as well as Fc- γ dependent antibody-dependent cell-mediated cytotoxicity (ADCC) in both murine IgG2a and human IgG1¹⁶. The YTE mutation was also incorporated to extend circulating half-life of the antibodies¹⁷. RGS worked with Vanderbilt University Medical Center (VUMC), Just-Evotec, ATUM, and Seromyx to develop the ADM03820 anti-SARS-CoV-2 mAbs.

A GLP repeat dose toxicity study was performed to evaluate the safety of ADM03820 in rats when administered by intramuscular injection or intravenous infusion once weekly for three weeks and to evaluate toxicity and reversibility of effects after a 72-day recovery period.

2.1.4. Public Readiness and Emergency Preparedness Act

This protocol and the study product tested are covered under the Public Readiness and Emergency Preparedness (PREP) act. The PREP Act provides compensation to participants in the event of serious physical injury or death caused by covered drugs and vaccines, and liability protection for persons conducting the clinical trial and the manufacturer of the drug or vaccine.

The PREP act provides immunity for covered persons (such as Manufacturers, Distributers, Program planners and other qualified persons who prescribe, administer or dispense the study product) from tort liability, unless the injury was caused by willful misconduct.

¹⁶ Lo M, Kim HS, Tong RK, Bainbridge TW, Vernes J-M, Zhang Y, Lin YL, Chung S, Dennis MS, Zuchero YJY, Watts RJ, Couch JA, Meng YG, Atwal JK, Brezski RJ, Spiess C, Ernst JA. 2017. Effector-attenuating substitutions that maintain antibody stability and reduce toxicity in mice. *J Biol Chem* 292:3900–3908. https://doi.org/10.1074/jbc.M116.767749.

¹⁷ Yu XQ, Robbie GJ, Wu Y, Esser MT, Jensen K, Schwartz HI, et al. Safety, tolerability, and pharmacokinetics of MEDI4893, an investigational, extended-half-life, anti-staphylococcus aureus alpha-toxin human monoclonal antibody, in healthy adults. *Antimicrob Agents Chemother*. (2017) 61:e01020-16. doi: 10.1128/AAC.01020-16.

The PREP Act also authorized a "Covered Countermeasures Process Fund" to provide compensation to eligible individuals who suffer specified injuries from administration or use of a countermeasure pursuant to the declaration. Any requests for compensation must be filed within one year of administration or use of the countermeasure. Requests would go to the HRSA Preparedness Countermeasures Injury Compensation Program (http://www.hrsa.gov/cicp). Compensation may then be available for medical benefits, lost wages and death benefits to eligible individuals for specified injuries in accordance with regulations published by the Secretary. Eligibility for compensation and the injuries for which compensation may be available are further defined by regulation.

An individual who suffers a serious physical injury or death from the administration and use of the study product must first seek compensation from the Covered Countermeasures Process Fund. A serious physical injury means an injury that is life threatening, results in, or requires medical or surgical intervention to prevent, permanent impairment of a body function or permanent damage to body structure. Any compensation will be reduced by public or private insurance or worker's compensation available to the injured individual.

If no funds have been appropriated to the compensation program, the Secretary does not make a final determination on the individual's request within 240 days, or if the individual decides not to accept the compensation, the injured individual or his representative may pursue a tort claim in the US District Court for the District of Columbia, but only if the claim involves willful misconduct, is pled with particularity required under the PREP Act, verified, and accompanied by an affidavit by a physician who did not treat the individual and certified medical records. Any award is reduced by any public or private insurance or worker's compensation available to the injured individual. Awards for non-economic damages, such as pain, suffering, physical impairment, mental anguish, and loss of consortium are also limited. If the individual accepts compensation, or if there is no willful misconduct, the individual does not have a tort claim that can be filed in a US Federal or a State court.

2.2. Rationale for Use of ADM03820

Antibodies from convalescent patients have been shown to lower or mediate the infectivity of the virus¹⁸, and their presence in respiratory mucosa may also protect ACE2 receptor-presenting cells. Studies performed at VUMC showed that antibodies that block attachment of the virus to Hace2-presenting host cells by binding to the region of the receptor-binding domain of the S protein (SRBD) demonstrated neutralizing activity in a rapid screening assay with authentic SARS-CoV-2¹⁹. Further analysis demonstrated that the SARS-CoV-2 SRBD contained three major antigenic sites. By utilizing antibodies non-competitively binding to different antigenic

¹⁸ Ou et al. Characterization of spike glycoprotein of SARS-CoV-2 on virus entry and its immune cross-reactivity with SARS-CoV. *Nat Commun.* 2020 Mar 27;11(1):1620.

¹⁹ Crowe JE, Carnahan RH, Zost SJ, Gilchuk P, et al. Potently neutralizing human antibodies that block SARS-CoV-2 receptor binding and protect animals. *bioRxiv*. 2020 May 22. https://doi.org/10.1101/2020.05.22.111005. [Epub ahead of print]

sites the researchers were able to demonstrate synergistic response potentially lowering the dose of each mAb three-fold¹⁹. The long mean incubation time of the disease also provides a prolonged time for inactivation by circulating systemic antibodies. Therefore, there is a strong rationale for developing monoclonal antibodies (mAbs) derived from convalescent COVID-19 patient sera directed against S proteins, and perhaps a combination of multiple antibodies, some directed to the S1/S2 site.

ADM03820 is a 1:1 mixture of two human IgG1 non-competitive binding anti-SARS-CoV-2 antibodies, mAb2130 (YTE+LALA) and mAb2381 (YTE+LALA), individually expressed in a Chinese hamster ovary (CHO) cell line. Several amino acid changes in the Fc region have been incorporated into mAb2130 (YTE+LALA) and mAb2381 (YTE+LALA) to silence or reduce the effector function of antibodies. The LALA variant eliminates complement binding and fixation as well as Fc- γ dependent antibody-dependent cell-mediated cytotoxicity (ADCC) in both murine IgG2a and human IgG1.¹⁶ The YTE mutation was also incorporated to extend circulating half-life of the antibodies.¹⁷

The proposed starting dose for ADM03820 dose escalation (150 mg IM) is based on previous toxicology studies, known safety profile of mAbs, and the expected potency of ADM03820. Based on the expected potency of ADM03820, the doses proposed for evaluation are anticipated to support PK analysis with microneutralization values (TCID₅₀) in therapeutic window for a prophylactic. Provided there are no safety concerns, dosing will escalate to 300 mg and 600 mg IM.

2.3. Potential Risks and Benefits

2.3.1. Potential Risks

The potential risks to the subjects due to participation in the study are those related to venipuncture, the IM injection, the administration of ADM03820, and a theoretical possibility of enhanced disease by antibody-dependent enhancement (ADE).

Venipuncture

Venipuncture causes transient discomfort and may cause fainting. Bruising at the site of the venipuncture may occur but can be prevented or lessened by applying pressure for several minutes. Infection at the site is possible but highly unlikely as aseptic technique must be employed.

IM Injection

An IM injection may cause some discomfort at the injection site. Other risks may include pain, redness, swelling, or warmth at the injection site. These risks are minimal.

An IM injection into the gluteus medius may cause sciatic nerve damage, bleeding, hematoma, or infection.

Effects of ADM03820

As ADM03820 has not been administered to humans, the potential risks are primarily based on adverse events associated with administration of other antibody products, especially infusion reactions.

Immunogenicity, the elicitation of antibodies directed against ADM03820 may occur following injection. ADM03820 is a combination of two human IgG1 antibodies, which based on experience with other humanized or chimeric mAbs, reduces the immunogenic potential.

ADE of virus infection of cells or disease in animal models occurs with other coronaviruses. Low levels of antibody directed against SARS-CoV-2 may increase virus infection of human cells cultured in the laboratory. Some studies have shown that administration of antibodies directed against SARS-CoV-2 can increase the severity of disease or levels of the virus in challenged animals. Although ADE of SARS-CoV-2 infection or COVID-19 has not been shown to occur in humans, the LALA mutation in ADM03820, by reducing potential Fc-receptor binding of ADM03820-SARS-CoV-2 complexes, may mitigate this potential risk.²⁰

2.3.2. Known Potential Benefits

This trial has no benefit for the subjects participating in the trial. The knowledge gained in this trial may help society, especially those exposed to, or at risk of being exposed to COVID-19.

3. OBJECTIVES

3.1. Study Objectives

Primary Objective:

• To assess the safety and tolerability of different doses of ADM03820 in healthy adult subjects.

Secondary Objective:

• To assess the pharmacokinetic (PK) and immunogenicity of different doses of ADM03820 in healthy adult subjects.

3.2. Study Outcome Measures

3.2.1. Primary Endpoints

- The occurrence of Serious Adverse Events following administration of ADM03820 to the final follow-up visit.
- The occurrence of Adverse Events from administration of ADM03820 to the final follow-up visit.

²⁰ Eroshenko, N., Gill, T., Keaveney, M. Church, et al., Implications of Antibody-Dependent Enhancement of Infection for SARA-CoV-2 Countermeasures. *Nature biotechnology*. 05 June 2020. https://www.nature.com/articles/s41587-020-0577-1

• The occurrence of changes from baseline in physical examination, vital signs and clinical safety laboratory values following administration of ADM03820 to the final follow-up visit.

3.2.2. Secondary Endpoints

- The assessment of C_{max} , T_{max} and $AUC_{(0-t)}$ for total antibodies of ADM03820 as measured by enzyme-linked immunosorbent assay (ELISA) for samples from Cohorts 1 and 2. The assessment of C_{max} , T_{max} and $AUC_{(0-t)}$ for each of the monoclonal antibodies of ADM03820 as measured by enzyme-linked immunosorbent assay (ELISA) for samples from Cohort 3, Cohort 4, and Cohort 5.
 - Pharmacokinetic samples will be tested by ELISA at pre-dose, 2, 4, 8, and 24 hours post dose, and on Days 3, 4, 8, 15, 30, 45, 60, 90, 120, 150, 180, and 365 for all cohorts
 - Samples will be tested by Microneutralization at pre-dose and Days 2, 15, 30, 60, 90, 120, 150, and 180 for all cohorts
- Samples will be tested by Electrochemiluminescence Assay (ECLA) to evaluate presence of anti-drug antibodies (ADA) collected for all cohorts.
 - ADA samples will be tested at pre-dose, and Day 15, 30, 45, 60, 90, 120, 150, 180, 365 for all cohorts
- Incidence of the first case of SARS-SoV-2 RT-PCR positive symptomatic illness occurring after dosing through Day 365
- Incidence of SARS-CoV-2 RT-PCR positive severe or critical symptomatic illness occurring after dosing through Day 365
- Incidence of COVID-19 related Emergency Department visits occurring after dosing through Day 365

4. STUDY DESIGN

This is a Phase 1, randomized, double-blind, placebo-controlled study of five dose cohorts to evaluate the safety, tolerability, and immunogenicity of ADM03820 in healthy adults. This is a first-in-human study and each subject will receive a single dose of ADM03820 or placebo.

The study will randomize a total of 50 healthy subjects to receive an intramuscular (IM) injection of either ADM03820 or placebo.

Cohort	Dose of ADM03820	Number of Subjects
1	150 mg IM injection	10 subjects (8 active, 2 placebo)
2	300 mg IM injection	10 subjects (8 active, 2 placebo)

Table 1: Cohorts

3	300 mg IM injection	10 subjects (8 active, 2 placebo)
4	300 mg IM injection	10 subjects (8 active, 2 placebo)
5	600 mg IM injection	10 subjects (8 active, 2 placebo)

Schedule for Subjects

Subjects in cohorts 1-4 will participate in the study for approximately 554 days, including a 14day screening period. Subjects in cohort 5 will participate in the study for approximately 379 days, including a 14-day screening period. All subjects in the study will have a 24-hour stay in the clinic after dosing is complete to ensure that no hypersensitivities or safety signals occur. Follow-up outpatient visits for all cohorts will occur on Days 3, 4, 8, 15, 30, 45, 60, 90,120, 150, 180, and 365 with cohorts 1-4 having additional telephone visits on Days 450 and 540. The last outpatient follow up visit is scheduled at Day 365. The end of the study is defined as the date of the last visit of the last subject in the study.

There are several blinded interim analyses planned for this study. A blinded interim analysis is planned to analyze all PK samples through Day 30 for all subjects in Cohorts 1-2. A second blinded interim analysis is planned to analyze all PK samples after all subjects in Cohorts 1-3 complete Day 60. A third interim analysis is planned to analyze safety and PK after all subjects in cohort 5 complete Day 60.

There is also an interim clinical study report (CSR) planned after subjects in Cohorts 1 through 4 complete Day 90.

Schedule for Cohorts

Since this is a first-in-human study, administration of the study products to subjects in cohorts 1, 2 and 5 will occur to allow careful observation of individuals for adverse events. Two sentinel subjects within each cohort will be admitted and administered a dose on Day 1 to remain in the clinic until Day 2. The randomization scheme will be designed to ensure that one subject will receive ADM03820 and the other will receive placebo. The IM dosing of the remaining subjects within cohorts 1, 2, and 5 will not be initiated until at least 48 hours have passed and no adverse events have occurred that meet halting criteria, and no safety signals have occurred that in the opinion of the investigator warrant further investigation. The remaining subjects within each specific cohort will be dosed at least four hours apart until all subjects in the cohort have been dosed. An alternate subject will be admitted to the unit for each two-subject group. Dose escalation will not occur until safety data through Day 8 is reviewed by the SRC.

Cohort 1 (150 mg IM injection) will be dosed first. Two sentinel subjects (one ADM03820 and one placebo) will each be administered a single 3 mL IM injection. The dosing of the next subjects within Cohort 1 will not be initiated until at least 48 hours have passed and no adverse events have occurred that meet halting criteria and no safety signals have occurred that in the

opinion of the investigator warrant further investigation. The remaining subjects in the cohort will be dosed at least four hours apart until all subjects in the cohort have been dosed.

Dose escalation to Cohort 2 will not occur until safety data through day 8 for Cohort 1 is reviewed by the SRC. Objective dose escalation criteria and safety evaluations will be utilized.

In Cohort 2 (300 mg IM injection), two sentinel subjects (one ADM03820 and one placebo) will each be administered two 3 mL IM injections. Dosing for the remaining subjects in Cohort 2 will be initiated after at least 48 hours have passed and no adverse events have occurred that meet halting criteria and no safety signals have occurred that in the opinion of the investigator warrant further investigation. The remaining subjects in the cohort will be dosed at least four hours apart until all subjects in the cohort have been dosed.

Dosing for Cohort 3 (300 mg IM injection) will not occur until safety data through day 8 for Cohort 2 is reviewed by the SRC. Objective safety evaluations will be utilized. Subjects in Cohort 3 will be scheduled based on the SRC recommendation and will each be administered two 3 mL IM injections without delay.

Dosing for Cohort 4 (300mg IM injection of drug product concentrated at 100mg/mL) will occur without delay. Subjects in Cohort 4 will be administered a single 3mL IM injection.

In Cohort 5 (600 mg IM injection of drug product concentrated at 100mg/mL), two sentinel subjects (one ADM03820 and one placebo) will each be administered two 3 mL IM injections. Dosing for the remaining subjects in Cohort 5 will be initiated after at least 48 hours have passed and no adverse events have occurred that meet halting criteria and no safety signals have occurred that in the opinion of the investigator warrant further investigation. The remaining subjects in the cohort will be dosed at least four hours apart until all subjects in the cohort have been dosed. The SRC will review safety data through day 8 for subjects in cohort 5 prior to the initiation of the phase 2 protocol.

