5.3. Treatment Assignment Procedures

5.3.1. Randomization Procedures

Randomized treatment assignments will be generated by a statistician at ICON. Randomization will occur following admittance to the unit and confirmation of eligibility is confirmed.

This is a Phase 1 double-blinded, placebo-controlled trial that will randomize subjects within five dosing cohorts to either active or placebo.

Cohorts 1, 2, and 5

For cohorts 1, 2, and 5, the first two subjects will be randomized in a 1:1 fashion to active and placebo to ensure that one of the first two subjects receives active treatment and the other control. An alternate subject will be admitted to the unit for each two-subject group. If one of the first two subjects is not randomized for any reason, then the alternate subject will receive the next consecutive randomization number. The product assignment of the remaining subjects in each cohort will follow a 7:1 randomization of active to placebo, respectively. The randomization list will be generated by the unblinded study biostatistician and uploaded to IRT

system by vendor (4G Clinical). Upon confirming eligibility of subjects, site research personnel will randomize subjects then the unblinded study pharmacist will be notified of treatment allocation via system-generated email.

Cohort 3 and 4

Subjects in cohort 3 and 4 will be randomized in a 4:1 ratio of active to placebo. The randomization list will be generated by the unblinded study biostatistician and uploaded to IRT system by vendor (4G Clinical). Upon confirming eligibility of subjects, site research personnel will randomize subjects then the unblinded study pharmacist will be notified of treatment allocation via system-generated email.

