6. STUDY PRODUCTS

6.1. Description of Study Products

ADM03820 is a 1:1 mixture of two human IgG1 non-competitive anti-SARS-CoV-2 antibodies formulated as 50 mg/mL or 100 mg/mL strength solutions in a 2 mL vial for IM administration. The drug product is a clear to opalescent, slightly colored, sterile aqueous solution at Ph 6. ADM03820 is formulated in 141 Mm L-arginine, 10 Mm sodium succinate buffer, with 0.25% v/v Polysorbate 80 and is filled as 1.2 mL in a 2 mL vial (50 mg/mL) or 1.7 mL in a 2 mL vial (100 mg/mL).

Placebo is 0.9% Sodium Chloride Injection, USP is a sterile, nonpyrogenic, isotonic solution of sodium chloride and water for injection.

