6.3. Formulation, Packaging, and Labeling

ADM03820

ADM03820 is a 1:1 mixture of two human IgG1 non-competitive anti-SARS-CoV-2 antibodies formulated as 50 mg/mL or 100 mg/mL strength solutions in a 2 mL vial for IM administration. The drug product is a clear to opalescent, slightly colored, sterile aqueous solution at Ph 6. ADM03820 is formulated in 141 Mm L-arginine, 10 Mm sodium succinate buffer, with 0.25% v/v Polysorbate 80 and is filled as 1.2 mL in a 2 mL vial (50 mg/mL) or 1.7 mL in a 2 mL vial (100 mg/mL).

The drug product will be supplied in 2-mL, pyrogen-free, Type 1 glass vials fitted with Tefloncoated butyl rubber stoppers and flip-up aluminum seals.

ADM03820 will be administered by intramuscular (IM) injection as follows: 150 mg (Cohort 1 as 1 x 3 mL IM injection) or 300 mg (Cohorts 2 and 3 as 2 x 3 mL IM injections or Cohort 4 as 1 x 3mL IM injection) or 600 mg (Cohort 5 as 2 x 3 mL IM injections).

Placebo (Normal Saline, 0.9% Sodium Chloride, USP)

0.9% Sodium Chloride Injection, USP is a sterile, nonpyrogenic, isotonic solution of sodium chloride and water for injection. Each mL contains sodium chloride 9 mg and contains no preservatives, bacteriostatic, antimicrobial agent, or added buffer. The solution is clear in appearance with a Ph range of 4.5 to 7.0.

Placebo will be administered by intramuscular (IM) injection as follows: 150 mg (Cohort 1 as 1 x 3 mL IM injection) or 300 mg (Cohorts 2 and 3 as 2 x 3 mL IM injections or Cohort 4 as 1 x 3mL IM injection) or 600 mg (Cohort 5 as 2 x 3 mL IM injections).

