6.4. Product Storage and Stability

ADM03820

Cohorts 1-3

ADM03820 drug product (50mg/mL) will be shipped frozen and should be stored at -90°C to -70°C until time of preparation. If a vial is removed from the freezer it must be used within 1 hour of thawing. If not used, it must be quarantined and maintained for study product accountability as per Section 6.6. ADM03820 should be protected from direct sunlight.

ADM03820 is not light sensitive under normal shipping and storage conditions. Avoid vigorous shaking or agitation.

Cohorts 4 and 5 Only

ADM03820 (100mg/mL) drug product will be shipped and should be stored at 2°C to 8°C until time of preparation. If a vial is removed from the refrigerator it must be used within 30 minutes. If not used, it must be quarantined and maintained for study product accountability as per Section 10.5. ADM03820 should be protected from direct sunlight. ADM03820 is not light sensitive under normal shipping and storage conditions. Avoid vigorous shaking or agitation.

Placebo (Normal Saline, 0.9% Sodium Chloride, USP)

Store at 20°C to 25°C (68°F to 77°F) [See USP Controlled Room Temperature; excursions between 15°C and 30°C (59°F and 86°F) are permitted]. Protect from freezing.

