9.5. Halting Rules

9.5.1. Halting Criteria for the Study

Study dosing can be halted at any time if medically indicated. Study dosing must be stopped, and a review of available safety data will be conducted by the SRC if any of the following occur:

- 1. Death of a dosed subject following injection and prior to the subject's last visit that was not the result of trauma or accident, and possibly related to study product.
- 2. Occurrence of a life-threatening allergic/hypersensitivity reaction (anaphylaxis) in any subject, manifested by bronchospasm with or without urticaria or angioedema or requiring hemodynamic support with pressor medications or mechanical ventilation.
- 3. One subject with an SAE that is considered possibly related or definitely related to study product.
- 4. Two or more subjects with a Grade 3 AE in the same organ class (systemic toxicity, clinical laboratory tests or vital signs) regardless of relatedness to study drug. An

exception to this includes scenarios where there are obvious and acceptable physiological explanations for a Grade 3 abnormality (e.g., Grade 3 hematuria in a menstruating female).

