9.5.3. Evaluation of Dose Escalation

The SRC must agree unanimously on the following criteria prior to dose escalation:

- A review of all available unmonitored and uncoded safety data from at least 7 subjects per cohort to Day 8, at a minimum, demonstrate that study halting criteria as outlined in Section 9.5.2 have not been met.
- A review of all available unmonitored and uncoded safety data from at least 7 subjects per cohort to Day 8, at a minimum, demonstrate that no safety signals of any nature were observed.

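### Cohort 4 is the first to receive the 100 mg/mL product, at twice the dose per injection site, without staggered dosing, and the SAP does not guarantee that its local reactions are reported separately

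*Protocol*

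**What the plan says.** **Product and injection.** Protocol Section 4 says that "Dosing for Cohort 4 (300mg IM injection of drug product concentrated at 100mg/mL) will occur without delay", as a single 3 mL injection. Section 6.3 sets out the 300 mg schemes: "300 mg (Cohorts 2 and 3 as 2 x 3 mL IM injections or Cohort 4 as 1 x 3mL IM injection". Section 6.1 gives one formulation for both strengths: "ADM03820 is formulated in 141 Mm L-arginine, 10 Mm sodium succinate buffer, with 0.25% v/v Polysorbate 80". Under Section 6.4, Cohorts 1 to 3 use frozen 50 mg/mL product. For Cohorts 4 and 5, "ADM03820 (100mg/mL) drug product will be shipped and should be stored at 2°C to 8°C until time of preparation".

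**Staggering.** Section 4 explains that "administration of the study products to subjects in cohorts 1, 2 and 5 will occur to allow careful observation of individuals for adverse events". It applies the sentinel pair, the 48-hour hold and the four-hour spacing to those three cohorts. Section 5.3.1 adds: "Subjects in cohort 3 and 4 will be randomized in a 4:1 ratio of active to placebo". Neither of these two cohorts has a 1:1 first pair.

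**Stopping.** Item 4 of Section 9.5.1 is triggered by "Two or more subjects with a Grade 3 AE in the same organ class (systemic toxicity, clinical laboratory tests or vital signs"). Section 9.5.2 acts between cohorts and does not exclude injection-site events. Section 9.5.3 requires review of data "from at least 7 subjects per cohort to Day 8" before escalation.

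**Reporting.** Protocol 11.3.3.1 and 11.3.3.2 present adverse events, vital signs, examinations and laboratory values by dose cohort and control group. The SAP's Safety analysis section presents all safety data by treatment group. The SAP never defines that term. Its PK population and Subject disposition paragraphs list it alongside dose cohort, as something separate. Its section on changes from the protocol declares only the added per-protocol population.

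**The concern.** The protocol staggers dosing so that individuals can be watched closely in a first-in-human study. Cohort 3 can reasonably skip this, because it repeats Cohort 2's product, dose and injection scheme after a safety review. Cohort 4 repeats only the total dose. Strength, storage form and amount per injection site are all new. Cohort 5 uses the same product at the same 300 mg per site and does have sentinels, but it comes after eight active subjects in Cohort 4 were planned to receive that product without them.

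Tolerability is part of the primary objective. Two things are at stake. One is how many subjects can be exposed to the new presentation before anyone has been observed for two days. The other is whether a difference in injection-site reactions between one 300 mg injection and two 150 mg injections would show in the tables.

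**Working it through.** **The plan's own figures.** Section 11.1 gives the probability of at least one event among 8 active subjects, and an exact upper bound when none occurs.
- 1 − (1 − 0.15)^8 = 0.728 and 1 − (1 − 0.5)^8 = 0.996.
- 1 − 0.025^(1/8) = 0.369.

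All three reproduce. They concern any toxicity event and do not bear directly on Cohort 4.

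**Dose per injection site** (strength × 3 mL; Sections 4, 6.3 and 6.4)

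| Cohort | Strength | Injections | mg per site | Total mg | Total mL |
|---|---|---|---|---|---|
| 1 | 50 mg/mL | 1 | 150 | 150 | 3 |
| 2, 3 | 50 mg/mL | 2 | 150 | 300 | 6 |
| 4 | 100 mg/mL | 1 | 300 | 300 | 3 |
| 5 | 100 mg/mL | 2 | 300 | 600 | 6 |

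From Cohorts 2 and 3 to Cohort 4, the dose per site doubles (300/150 = 2), the total dose is unchanged and the volume halves (3/6).

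**Exposure before 48 hours of observation.** As written, all 8 active Cohort 4 subjects can be dosed. Under the Cohort 1/2/5 procedure, 1 can.

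**Illustration only.** Let p be the chance of a local reaction bad enough to stop dosing. The documents give no such rate, so p is assumed. The range 0.15 to 0.5 is borrowed from Section 11.1's any-toxicity rates, and 0.05 is added as a rarer case. Assume also that a reaction in the active sentinel stops dosing for good, on the investigator's judgment.
- All dosed together: 8p expected affected.
- With a sentinel hold: p + (1 − p) × 7p.
- Difference: 7p².

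| p | Together | Sentinel hold | Difference |
|---|---|---|---|
| 0.05 | 0.40 | 0.38 | 0.02 |
| 0.15 | 1.20 | 1.04 | 0.16 |
| 0.30 | 2.40 | 1.77 | 0.63 |
| 0.50 | 4.00 | 2.25 | 1.75 |

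The difference depends on the square of an unknown rate, so the table shows the shape of the benefit and does not estimate it. A credit for four-hour spacing is left out. It would need the two-subject stop in 9.5.1 item 4 to cover local reactions, which that item does not name.

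**What merging would do.** If treatment group means dose, the 300 mg column holds 3 × 8 = 24 active subjects: 16 with two 150 mg injections and 8 with one 300 mg injection. Cohort 4 is then 8/24, one third of the column. If it means active against placebo, Cohort 4 is 8 of 5 × 8 = 40, one fifth.

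**The case against.** **Sentinels follow total dose.** They are used at 150, 300 and 600 mg, each a new total dose. Cohort 4 repeats a dose planned for 16 active subjects in Cohorts 2 and 3, with the same listed excipients and half the volume. Nothing in the documents suggests worse local reactions at 100 mg/mL. This stands, and it limits the point to local tolerability and a new presentation. A reader might infer an unguarded systemic escalation; the unchanged 300 mg total rules that out.

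**Cohort 4 is not unprotected.** Section 9.5.1 allows dosing to be halted at any time on medical grounds, and one related SAE or an anaphylactic reaction stops it. A physician is present, each subject is directly observed for 30 minutes, and all stay 24 hours. This stands too. Eight is therefore the most the text permits, not a forecast. None of these measures, however, separates the first active subject from the other seven.

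**Safety Review Committee.** A reader might also count as a defect that no committee review is named before Cohort 4. That does not hold up. The protocol's general gate concerns dose escalation, and this step is 300 mg to 300 mg. Such a review would contain only 50 mg/mL data and could not inform on the new product. Sections 9.5.2 and 9.5.3 already bring Cohort 4 data to Day 8 into the decision on Cohort 5.

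**Pooling is not stated.** No sentence in the SAP says that Cohorts 2 to 4 will be combined. Individual listings are planned, ADA is compared among cohorts, and the table shells are in a separate document. So pooling is something the wording allows, not something it announces. Still, an undefined term that the SAP sets apart from dose cohort replaces the protocol's explicit grouping, and the change is not declared.

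**It may be too late.** The summaries of changes show Cohort 4 added in version 5.0 and Cohort 5 in version 6.0, while version 7.0 only shortens Cohort 5 follow-up. This suggests that Cohort 4 has been dosed, but no dosing dates are given.

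**Conclusion.** The concern holds as one of local tolerability. Cohort 4 introduces a new strength, a new storage form and twice the dose per site, yet lacks the staggering that the protocol gives to Cohorts 1, 2 and 5. The firm size is 8 active subjects, against 1, who can be dosed before any has 48 hours of observation. No number of reactions avoided can be claimed. Under assumed rates the saving runs from 0.02 to 1.75 subjects and is negligible at the low end.

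The reporting gap matters most, because it applies whatever the dosing status and touches the primary objective. It rests on reading treatment group as the SAP uses it elsewhere, separate from dose cohort. The halting-rule point rests on item 4's list being complete as printed: it names systemic toxicity, laboratory tests and vital signs, and no local reactions.

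**What to change.** 1. **SAP, general safety text and 8.7, in all cases.** Replace treatment group with dose cohort and pooled placebo, in line with protocol 11.3.3.1 and 11.3.3.2 (the protocol says control group; one combined placebo group is the natural reading). Show Cohort 4 injection-site events apart from Cohorts 2 and 3. Cost: a wording change and additional table columns.
2. **Protocol 9.5.1 item 4, for any cohort still to be dosed.** Add Grade 3 injection-site reactions. Cost: an amendment of one line.
3. **Protocol Sections 4 and 5.3.1, only if Cohort 4 is not yet dosed.** Use one active and one placebo sentinel, a 48-hour hold, then 7:1 randomization with four-hour spacing. Cost: an amendment, a revised Cohort 4 randomization list, and at least 48 + 7 × 4 = 76 hours (seven gaps among the remaining eight subjects). No extra subjects, visits or samples are needed.

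If Cohort 4 has been dosed, items 1 and 2 remain, with item 2 serving Cohort 5. If Cohort 5 has been dosed as well, only item 1 remains.
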